- For participants in the single-message and 3-messages and 1-week delay conditions, they viewed the anti-smoking messages at baseline. They received the pro-smoking ad 1 week later, and the post-exposure outcome measures were collected at 1 week.
- For participants in the single-message and 3-messages and 1-month delay conditions, they viewed the anti-smoking messages at baseline. They received the pro-smoking ad 1 month later, and the post-exposure outcome measures were collected at 1 month.

Figure 3. Pro-smoking Ads

Primary Outcome Measures

1. Intention to quit smoking (among people who currently smoke)

We used a 4-item scale on intention to quit smoking at baseline and at follow-up (immediate, one-week and one-month) among current smokers only using four items:

- a. I will make an effort to quit smoking in the next 30 days;
- b. I intend to quit smoking in the next 30 days;
- c. I expect to quit smoking in the next 30 days;
- d. How likely is it that you will quit smoking in the next 30 days. Responses ranged on 7-point Likert-like scales.

Responses were summed to create a scale for intention to quit (range from 4-28), higher scores indicate higher intention to quit.

Note: Intent to quit smoking was not collected after exposure to the pro-tobacco message in the no-message, 1-message, and 3-message immediate conditions among people who currently smoked.

2. Intention to purchase cigarettes

The Juster scale was used to measure intention to purchase cigarettes at baseline and at one-month follow-up. Participants were asked, "How likely are you to purchase cigarettes in the next 6 months?" Responses ranged from 0=No chance, almost no chance (1 in 100) to 10=Certain, practically certain (99 in 100). Higher values reflect higher intention to purchase.

Note: Intent to purchase cigarettes was not collected after exposure to the pro-tobacco message in the no-message, 1-message, and 3-message immediate conditions among people who currently smoked and people who did not smoke.

3. Susceptibility to Smoke Cigarettes (among people who currently do not smoke)

Susceptibility to smoke cigarettes was measured among people who do not currently smoke using four-items:

- a. Have you ever been curious about smoking a cigarette?
- b. Do you think you will smoke a cigarette in the next year?
- c. Do you think that you will try a cigarette soon?

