Data analysis plan. We will compare covariate distributions across conditions to evaluate the extent to which randomization was successful. Our main analytic strategy is to fit linear regression models to predict the primary and secondary outcomes immediately after exposure to the pro-tobacco message by experimental condition, stratified by smoking status. This regression-based approach allows us to adjust the effect of message condition for factors that may not have been well balanced by randomization (including baseline values of the outcomes), as well as to explore potential interactions between experimental condition and baseline covariates, which can further inform message development. Let Y_i be the outcome (e.g. intention to quit among smokers) for subject i , x_i be the assigned message condition, and c_i be a vector of individual, meso-, and macro-level covariates. We will fit linear regression models of the form

$$\mathbb{E}(Y_i|x_i, c_i) = \alpha + \beta'x_i + \gamma'c_i$$

where β is a vector of coefficients associated with each treatment condition and γ vector of coefficients associated with the covariates. Each $\hat{\beta}$ is interpretable as the average difference in the outcome immediately after exposure to the pro-tobacco message for that treatment condition, vs. the control condition, adjusting for baseline covariates. All planned comparisons will be tested using two-tailed tests at a Bonferroni-corrected $P<0.05$ cutoff.

To account for differential loss to follow-up by treatment arm, we will apply inverse probability of censoring weighting as follows. For each experimental condition, we will estimate the probability of loss to follow-up at the time of the outcome measurement conditional on covariates using logistic regression. Based on these models, we will generate inverse probability of censoring weights and fit weighted models for the primary and secondary outcomes using a generalized estimating equations (GEE) approach. Under the assumption of Missingness At Random (MAR), these models will yield unbiased and consistent estimates of the treatment effects of interest.

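### For quit and purchase intention, the planned post-ad model can estimate no effect versus control and no delayed-versus-immediate effect, because the control and both immediate arms have no outcome at that time

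*Combined protocol and SAP*

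**What the plan says.** **Model.** Under Statistical Analyses, Data analysis plan, linear regressions will "predict the primary and secondary outcomes immediately after exposure to the pro-tobacco message by experimental condition, stratified by smoking status". Each coefficient "is interpretable as the average difference in the outcome immediately after exposure to the pro-tobacco message for that treatment condition, vs. the control condition". The section gives intention to quit among smokers as its example of the outcome.

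**Data collected.** Under Primary Outcome Measures, the note to item 1 states: "Intent to quit smoking was not collected after exposure to the pro-tobacco message in the no-message, 1-message, and 3-message immediate conditions", for people who smoke. The note to item 2 states: "Intent to purchase cigarettes was not collected after exposure to the pro-tobacco message in the no-message, 1-message, and 3-message immediate conditions", for both smokers and non-smokers. Susceptibility and the secondary outcomes carry no such note.

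**Timing elsewhere.**
- Table 1 and the bullets on the ads describe, for outcomes in general, an assessment right after the ad in the no-message and immediate arms. Table 1 also gives every arm a 1-month assessment.
- The quit-intention item lists immediate, one-week and one-month follow-up.
- For purchase intention, "The Juster scale was used to measure intention to purchase cigarettes at baseline and at one-month follow-up"; no 1-week time is listed. Table 1 and the bullets do give the 1-week arms a general assessment at 1 week.

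**Hypotheses and multiplicity.** Study Hypotheses names three factor effects: three messages versus one, delay versus immediate, and boosters versus none. On multiplicity, "All planned comparisons will be tested using two-tailed tests at a Bonferroni-corrected" 0.05 cutoff; the comparisons are not listed.

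**The concern.** The model needs an outcome in the reference arm at the analysis time. For quit and purchase intention the notes say there is none. The same is true of both immediate arms, which one of the stated hypotheses needs as comparator. The notes disclose the gap in collection, but the analysis section was not adapted: it names no other time, reference arm or contrast for these outcomes.

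As written, the analyst would have to choose the time point, the reference and the number of tests after data collection. If the control arm's 1-month value were used without comment, the plan's own wording would label the result an immediate post-ad effect. For the 1-month-delay arms it would in fact compare people who had just seen the ad with controls who saw it about a month earlier.

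**Working it through.** **Inputs.** Nine arms (Table 1). Arms empty at the post-ad time: no-message, single-immediate, three-immediate (notes to items 1 and 2). Enrolled: 1075 smokers and 1516 non-smokers, 2591 in all (Sample Enrollment). Attrition 20%, power 80%, two-sided 0.05 (Sample Enrollment). The plan lists no contrasts, so the enumeration below is mine, built from the arms and the hypotheses.

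**Estimability.** The arm part of the model is mean(arm) = α + β(arm), with α the control mean. A difference between two arms can be estimated only if both have outcome data; adjusting for covariates does not change this. With data in the six delayed arms only, the arm part has rank 6 of 9. With data in only the four 1-month arms, it has rank 4.

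| Contrast at the post-ad time | All arms observed | Six delayed arms | Four 1-month arms only |
|---|---|---|---|
| Arm vs control | 8 | 0 | 0 |
| Delayed vs immediate | 4 | 0 | 0 |
| Three vs single | 4 | 3 | 2 |
| Booster vs none | 2 | 2 | 2 |
| 1-month vs 1-week delay, no boosters | 2 | 2 | 0 |

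The middle column applies to quit intention, and to purchase intention if it was collected at 1 week. The last column applies to purchase intention if it was not.

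An additive factorial model does not help. Every delayed arm received a message and a delay, so those two effects are constant across the six arms and merge with the intercept. Dose, booster and 1-month-versus-1-week effects stay estimable.

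**Extent.** There are four primary outcome-by-stratum analyses: quit intention in smokers, purchase intention in smokers, purchase intention in non-smokers, and susceptibility in non-smokers. The first three are affected. Assuming equal allocation, 1075 × 3/9 ≈ 358 smokers have no post-ad quit intention and 2591 × 3/9 ≈ 864 participants have no post-ad purchase intention, before attrition.

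**Weights.** The plan will "estimate the probability of loss to follow-up at the time of the outcome measurement conditional on covariates using logistic regression" and weight by its inverse. That reweights people observed within an arm. Here a whole arm is unobserved by design, so its probability of observation is zero and no weight exists.

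**Time since the ad at the 1-month survey** (from Table 1):

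| Arms | Approximate time since ad |
|---|---|
| No-message, immediate | 4 weeks |
| 1-week delay | 3 weeks |
| 1-month delay, with or without boosters | just seen |

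Contrasts within a row have equal time since the ad. Contrasts across rows do not.

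**Precision of the surviving contrasts.** For smokers, n per arm = 1075/9 × 0.8 = 95.6, assuming equal arms and no covariate gain. With m arms on each side, detectable d = (z for two-sided α + 0.8416) × √(2/(95.6m)).

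| Divisor | α | One pair | Booster, 2 vs 2 arms | Dose, 3 vs 3 arms |
|---|---|---|---|---|
| 3 | 0.0167 | 0.47 SD | 0.33 SD | 0.27 SD |
| 5 | 0.0100 | 0.49 SD | 0.35 SD | 0.29 SD |
| 10 | 0.0050 | 0.53 SD | 0.37 SD | 0.31 SD |

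Pooling over schedules, which matches the factor hypotheses, detects a much smaller dose effect than any single pair of arms.

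**The case against.** The strongest reply is that the gap is disclosed and an all-arm time point is documented: the Study Protocol section describes a 1-month survey of the study outcomes, Table 1 gives every arm a 1-month assessment, and purchase intention is explicitly timed at one month. This stands in part. A 1-month analysis may well be possible, and for the 1-week arms the mismatch with control is only about one week. But the Data analysis plan does not name that time point, and the result would be a different estimand from the one it defines.

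It can also be said that Table 1 and the bullets on the ads speak of outcomes in general, so that the notes are simply exceptions. That is a fair reading, and those passages need only be reconciled. The sharper conflict is the immediate follow-up listed for quit intention: only the three arms named in the note see the ad at baseline, so under the note no arm has such a value.

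A reader might infer that nothing can be learned about quit or purchase intention, or that all outcomes are affected. The documents support neither. Dose and booster effects survive among the delayed arms, and no note restricts susceptibility or the secondary outcomes. Nor should all six delayed arms be treated as equally compromised at 1 month.

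**Conclusion.** The point holds and needs correction before the analysis is reported. For two of three primary outcomes, one of them the plan's own example, the stated estimand cannot be produced: 0 of 8 effects versus control and 0 of 4 delayed-versus-immediate effects at the planned time. The delay-versus-immediate hypothesis cannot be tested at that time for these outcomes. The dose and booster hypotheses can be, among the delayed arms.

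This rests on three readings:
- The control is the no-message arm.
- The notes' list means no-message, single-immediate and three-immediate. If the 1-message wording covered more single-message arms, more would be lost.
- The notes refer to the assessment in the baseline survey, not the 1-month survey. Table 1 and the Study Protocol section support this, but it needs confirming, and the 1-month contrasts depend on it.

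Non-estimability at the post-ad time does not depend on the allocation assumption; the counts of 358 and 864 and the detectable differences do.

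**What to change.** 1. State in the Data analysis plan that, for quit and purchase intention, post-ad effects versus control and delayed-versus-immediate effects cannot be estimated.
2. At the post-ad time, replace the eight coefficients with factor contrasts among the delayed arms that have data: three versus single pooled over delayed schedules, and booster versus none pooled over dose in the 1-month arms. Report 1-month versus 1-week delay without boosters as exploratory, because the hypothesis concerns delay versus immediate.
3. At 1 month, after confirming that the values exist, use contrasts with equal time since the ad: single-immediate versus none, three-immediate versus none, three versus single immediate, and three versus single within the 1-week arms. The last matters mainly for purchase intention if it was not collected at 1 week.
4. Label any 1-month comparison of delayed arms with control or immediate arms as mixing message or delay effect with time since the ad: about 3 versus 4 weeks for the 1-week arms, and just after the ad versus about a month for the 1-month arms.
5. Set the Bonferroni divisor to the number of confirmatory contrasts retained, fixed before results are seen. With one family per outcome and stratum, for example: two pooled contrasts alone, 0.05/2 = 0.025; with the three control and immediate-arm contrasts, 0.05/5 = 0.01; with the 1-week-arm dose contrast as well, 0.05/6 = 0.0083.
6. Label the change as made after data collection (recruitment ended July 2023; the document is dated July 2024).
7. Reconcile Table 1, the bullets on the ads and the immediate quit-intention time with the notes, and state whether purchase intention was collected at 1 week.

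**Cost.** No new data. These two outcomes lose the planned post-ad tests versus control and the delayed-versus-immediate tests, and the revised analysis is post hoc.

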Cover Page

Project RESIST: Evaluating the Effects of Anti-smoking Inoculation Messages Among Young Adult Sexual Minority Women

NCT05499520

Date July 5 2024

PROTOCOL TITLE: Project RESIST: Evaluating the Effects of Anti-smoking Inoculation Messages Among Young Adult Sexual Minority Women

Brief Background

This study is the second of two randomized controlled experiments within Project Resist. The first randomized controlled experiment evaluated the effects of LGBTQ-tailoring (using a campaign logo with LGBTQ+ Pride colors and a slogan indicating the campaign's focus is LGBTQ+ health) vs. a control condition (yellow campaign logo and a slogan indicating the campaign's focus is on health in general) on intentions to quit smoking (among current smokers only), intentions to purchase cigarettes, marketing receptivity, industry beliefs, and industry attitudes (both current and non-current smokers). The messages used highlighted anti-tobacco industry arguments (e.g., how the tobacco industry targets children) and health impacts of cigarette smoking (e.g., risks of smoking related illnesses). Results from this experiment have been reported ([NCT04812795](#) and [publication](#)).

In this experiment, we conducted a national online survey experiment among young adult cisgender and transgender SMW smokers and non-smokers to evaluate the effects of exposure to anti-tobacco-industry inoculation health messages that are tailored for LGBTQ+ audiences. We varied the dose (3 messages vs. single message vs. no message), latency (immediate vs. 1-week delay and 1-month delay), and boosters (3 weekly boosters vs. a single dose) of anti-smoking messages on smoking and quitting intentions. Participants were randomized to one of 9 experimental arms using a fractional factorial design. All messages used LGBTQ+ tailored messages and highlighted anti-tobacco industry arguments. Six of the 12 messages used were identical to those used in the first experiment described above and six messages were new messages that were created.

Study Hypotheses

We hypothesize that multiple exposures (3 vs. single), delayed exposure (1-week or 1-month vs. immediate), and booster exposures (3 boosters vs. none) of anti-tobacco industry inoculation health messages will be associated with increased resistance to marketing, reduced smoking susceptibility, reduced intention to purchase cigarettes, and increased quitting intention.

Sample Enrollment

[figure not shown]

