This study recruited young adult sexual minority women (SMW), ages 18-30 years, those who current smoke ($n = 1075$) and those who did not smoke ($n = 1516$). Participants were recruited through a combination of the Prolific online panel (~62% of the sample), The Population Research in Identity and Disparities for Equality (PRIDE) Study (~13%), social media advertising (paid Instagram ads and posting through LGBTQ+-serving community organizations' social media accounts) (~14%), and a dating app (HER) (~11%). Participants were asked to complete a baseline survey and then randomized to one of the 9 message conditions (see Experimental conditions table below). **Figure 1** summarizes the CONSORT flow diagram.

Our planned targeted enrollment was to recruit 1500 participants who currently smoke and 1500 who did not currently smoke (total $n=3000$). We used GPower (ver. 3) to estimate the effect sizes in the outcome variables as a function of message condition, assuming two-tailed tests, with 80% power and $\alpha=0.05$, and factored in 20% attrition among participants to arrive at the sample size of 3000.

However, we experienced difficulty in recruiting participants who currently smoke. Recruitment began in September 2022 and concluded in July 2023. In order to address slow recruitment for current smokers, we expanded the recruitment timeline, reached out to over 30 LGBT organizations to canvass over Pride month, flyering ads locally, advertised on social media and on the HER dating app. We further re-opened

the recruitment on the Prolific panel (having enrolled there ~6 months prior) and only received a handful of eligible cases so we ultimately decided to close out the recruitment to focus on the analysis for the remainder of the study.

Figure 1. CONSORT Flow Diagram

Study Protocol

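### Single-step Bonferroni is valid but gives up power; Holm keeps the same 0.05 familywise bound and never rejects less

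*Combined protocol and SAP*

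**What the plan says.** Under Statistical Analyses, the data analysis plan fits linear models separately by smoking status. Each coefficient is the adjusted difference in the post-threat outcome "for that treatment condition, vs. the control condition". On multiplicity it says only: "All planned comparisons will be tested using two-tailed tests at a Bonferroni-corrected" 0.05 cutoff. No step-down or correlation-based procedure is named. The number of comparisons in the family is not given, nor whether the family spans outcomes or smoking strata.

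Brief Background gives the design: "Participants were randomized to one of 9 experimental arms using a fractional factorial design". One arm is the no-message condition, so each model has eight coefficients against it. Study Hypotheses, however, names different contrasts: "multiple exposures (3 vs. single), delayed exposure (1-week or 1-month vs. immediate), and booster exposures (3 boosters vs. none").

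Sample Enrollment sizes the trial "assuming two-tailed tests, with 80% power" and alpha 0.05, with no mention of a multiplicity adjustment. The target was to "recruit 1500 participants who currently smoke and 1500 who did not currently smoke", and the sponsor "factored in 20% attrition among participants to arrive at the sample size of 3000". Actual enrolment was 1075 who smoke and 1516 who do not.

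Notes under Primary Outcome Measures say that intention to quit and intention to purchase were not collected after the pro-tobacco message in the no-message arm or the two immediate arms. No such note is attached to susceptibility or to the secondary outcomes.

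**The concern.** Single-step Bonferroni holds every test in the family at 0.05 divided by the family size, however many hypotheses have already been rejected. Where the comparisons share a control arm it also ignores their positive correlation, which is about 0.5 with equal arms. Both features cost power that another procedure can recover within the same 5% bound.

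Power matters here because the sizing paragraph mentions no multiplicity adjustment while the analysis applies one, and because the stratum of people who smoke fell short of its target. Recruitment is closed, so sample size can no longer make up the difference. The testing procedure is one of the few things left to choose.

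**Working it through.** **The plan's own figure.** The total of 3000 cannot be reproduced, because no effect size or SD is given. It can be solved backwards, assuming equal allocation:

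- Evaluable per arm per stratum: 1500 × 0.8 / 9 = 133.3.
- Detectable effect at 80% power, two-sided 0.05: d = (1.960 + 0.842) × √(2/133.3) = 0.343 SD.
- With eight comparisons the Bonferroni level is 0.05/8 = 0.00625, critical value 2.734. Power at 0.343 SD is Φ(2.802 − 2.734) = 53%.
- 80% power at that level needs (2.734 + 0.842) × √(2/133.3) = 0.438 SD.
- As enrolled, after 20% loss: 1075 × 0.8 / 9 = 95.6 per arm (smoke) and 1516 × 0.8 / 9 = 134.8 (do not smoke).

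**Why Holm cannot do worse.** Order the P values. Holm compares the smallest with 0.05/8, the next with 0.05/7, and so on up to 0.05, stopping at the first failure. The first threshold is Bonferroni's and later ones are larger, so every Bonferroni rejection is also a Holm rejection. Control at 0.05 holds under any dependence, so it needs no shared control, equal arms or particular family size.

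**Size of the gain.** Assumptions: eight two-sided tests against one control, equal arms, correlation 0.5, normal outcome with known SD. Step-down Dunnett uses critical values falling from 2.65 to 1.96. Simulated power per comparison (%):

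| Per arm | Effect (SD) | True effects | Bonferroni | Holm | Step-down Dunnett |
|---|---|---|---|---|---|
| 133.3 (planned) | 0.343 | 1 | 52.7 | 52.7 | 56.0 |
| 133.3 (planned) | 0.438 | 1 | 80.0 | 80.0 | 82.3 |
| 134.8 (do not smoke) | 0.343 | 4 | 53.2 | 56.3 | 59.3 |
| 134.8 | 0.343 | 8 | 53.4 | 64.3 | 66.6 |
| 134.8 | 0.438 | 4 | 80.5 | 83.3 | 85.1 |
| 134.8 | 0.438 | 8 | 80.5 | 89.6 | 90.6 |
| 95.6 (smoke) | 0.343 | 4 | 35.8 | 38.1 | 41.2 |
| 95.6 | 0.343 | 8 | 35.8 | 44.2 | 46.9 |
| 95.6 | 0.45 | 4 | 64.7 | 67.9 | 70.5 |
| 95.6 | 0.45 | 8 | 64.8 | 76.0 | 77.8 |

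With graded effects of 0.1 to 0.5 SD, mean power is 32.0 / 36.2 / 38.2 at 95.6 per arm and 43.2 / 48.7 / 50.4 at 134.8. With effects of 0.05 to 0.40 SD at 96 per arm it is 18.4 / 20.6 / 22.3. Mean gains under grading are therefore about 2 to 6 points for Holm (20.6 − 18.4 = 2.2; 48.7 − 43.2 = 5.5) and 4 to 7 for step-down Dunnett (22.3 − 18.4 = 3.9; 50.4 − 43.2 = 7.2).

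**Familywise error.** Under the global null with a shared control, Bonferroni and Holm run at about 4.0%, and step-down Dunnett at its nominal 5%. With four null arms: Bonferroni about 2.2%, Holm 3.1 to 3.6%, step-down Dunnett 3.7 to 4.3%.

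**Larger families.** For families of 16 to 40 tests, Holm gains 0 points with one true effect, about 1 to 4 with half of them true, and up to about 14 with all true.

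**Where the shared-control structure exists.** For quit and purchase intention, the no-message arm has no post-threat value, so the eight-comparison family in the analysis plan cannot be formed as written. It can be formed for susceptibility (people who do not smoke) and for the secondary outcomes. The rows at 95.6 per arm can therefore describe only the secondary outcomes.

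**The case against.** Bonferroni is valid, simple, and comes with matching simultaneous intervals. The gain is conditional: Holm returns nothing if only one condition works, and the largest figures need all eight effects to be real and equal, whereas the hypotheses expect results to differ by dose, latency and boosters. The family is undefined and has to be settled before any gain can be stated for this trial. Changing to a more liberal rule after enrolment ended (July 2023, against a document date of July 2024) invites doubt. All of this stands. It limits the size and grade of the point, but it does not make single-step Bonferroni the better test, because Holm's advantage does not depend on the family or the effects.

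The simulation also simplifies. It applies 20% loss to every arm, although the no-message and immediate arms have their post-threat measures in the baseline session. The correlation between delayed arms is then nearer 0.45, a small change. It also ignores baseline adjustment, so its absolute powers are not the plan's.

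A reader might infer more than the documents support:

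- *That any step-down method returns up to 13 points on every planned comparison.* In this family that figure belongs to step-down Dunnett with eight equal true effects.
- *That every planned comparison shares the control.* The dose, latency and booster contrasts do not use the no-message arm.
- *That the shortfall among people who smoke makes this pressing for their primary outcomes.* Those are quit and purchase intention, where the control lacks the post-threat measure. The one primary outcome with the full structure is in the stratum that met its target (1516 against 1500).
- *That Bonferroni protects nothing extra.* Only the 5% bound is the same; its actual error is lower.

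**Conclusion.** The point holds as a matter of efficiency. Holm dominates Bonferroni for testing at the same 0.05 familywise bound, whatever family the sponsor intends. For an assumed family of eight comparisons with the no-message arm, equal arms and effects of 0.343 to 0.45 SD, the gains per comparison are:

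| True effects | Holm | Step-down Dunnett |
|---|---|---|
| One | 0 points | about 2 to 3 |
| Four | about 2 to 3 | about 4 to 6 |
| Eight, equal | about 8 to 11 | about 9 to 13 |

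Graded effects gain less than eight equal ones. Family size and effect size are assumptions, because the documents state neither. The Dunnett column is relevant only to susceptibility in people who do not smoke and to the secondary outcomes. Nothing here makes the planned Bonferroni inference invalid.

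**What to change.** In the data analysis plan, replace the Bonferroni-corrected cutoff with Holm-adjusted P values at familywise 0.05. State the family in the same sentence: which comparisons, including any dose, latency and booster contrasts, and whether it spans outcomes and smoking strata.

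Step-down Dunnett (max-t, using the estimated covariance of the coefficients) may be named instead for comparisons with the no-message arm on susceptibility and the secondary outcomes. It should not be named for quit or purchase intention.

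The cost is a short edit and standard software. The drawback is that step-down tests have no simple matching simultaneous intervals, so report Bonferroni intervals beside the adjusted P values. Because recruitment has closed, date the change. If outcome data have already been seen, say so, label the change post hoc, and show the Bonferroni results as well.
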